5.3. Dosage and Administration of Study Drugs

All study drugs (Oral GS-6207, GS-6207 injection for SC administration, TAF, F/TAF, BIC, B/F/TAF) will be provided by Gilead.

Treatment Group 1 and 2 participants will be administered oral GS-6207 on Days 1, 2, and 8. GS-6207 will be administered without regards to food. The oral GS-6207 (300 mg) bottle will remain at investigator site and will not be given to the participants. Oral and SC dosing is presented in [Table 5-1](#).

Table 5-1. GS-6207 Dosing for Treatment Group 1 and 2

Study Visits	GS-6207
Day 1	600 mg oral
Day 2	600 mg oral
Day 8	300 mg oral
Day 15	927 mg SC
Week 28 and every 26 weeks thereafter	927 mg SC

GS-6207 927 mg injection will be administered in the abdomen via SC injections on Day 15, Week 28, and every 6 months (26 weeks) thereafter. GS-6207 should be administered as multiple injections at different abdominal sites no more than 15 minutes apart when possible.

In addition to GS-6207, Treatment Group 1 and 2 participants will take oral daily F/TAF from Day 1 onwards approximately at the same time. F/TAF will be administered on-site on Day 1. The F/TAF bottle(s) can be kept on-site for Day 2 administration and should be given to participants at the end of Day 2 visit to take at home from Day 3 onwards. Treatment Group 1 participants with < 50 copies/mL of HIV-1 RNA at Week 16 and Week 22 will stop F/TAF at Week 28 and will initiate oral daily TAF. Treatment Group 2 participants with < 50 copies/mL of HIV-1 RNA at Week 16 and Week 22 will stop F/TAF at Week 28 and will initiate oral daily BIC.

Oral dosing on Day 1, Day 2, and Day 8 and all SC GS-6207 administrations will occur on site and without regard to food (for Oral Bridging Period, see [5.4](#)).

If participants in Treatment Groups 1 and 2 are not dosed within the protocol visit windows, and the investigator believes that it is in the participant's medical interest to continue to receive GS-6207, Gilead should be contacted immediately, and the participant may continue to receive GS-6207 with the approval of the Gilead medical monitor. Additional oral GS-6207 doses may be needed prior to subsequent SC dosing (Section [5.4](#)).

Table 5-2. GS-6207 Dosing for Treatment Group 3

Study Visits	GS-6207
Day 1	600 mg oral
Day 2	600 mg oral
Day 3 onwards	50 mg oral daily

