3.1.3. Per-Protocol Analysis Set

The Per-Protocol (PP) Analysis Set is defined for the primary efficacy analysis. This analysis set includes all subjects in the FAS excluding subjects meeting any of the following criteria:

- Subjects who do not have on-treatment HIV-1 RNA in the Week 54 analysis window, except when missing is due to discontinuation of study drug for lack of efficacy. (Note: lack of efficacy is defined as having the check-box for Lack of Efficacy marked as the reason for premature study drug discontinuation on the study drug completion eCRF page.)
- Subjects who meet the exclusion criterion that was known hypersensitivity to the study drug(s), the metabolites, or formulation excipient.
- Subjects who meet the exclusion criterion for receiving treatment within 3 months prior to screening, or anticipated treatment during the study period with immunosuppressant therapies, hydroxyurea, foscarnet, radiation, or cytotoxic chemotherapeutic agents that listed in Table 5-3 in protocol Section 5.4.
- Nonadherence to once daily (QD) study drug(s): subjects with adherence rate for active once daily study drug(s) up to the Week 54 Visit below the 2.5th percentile

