4.2.2. Adherence to Study Drug

4.2.2.1. Adherence to SC LEN

The adherence to SC LEN will be assessed by adherence to the projected injection interval, which is 26 weeks (182 days) between 2 adjacent injection visits. The number of days from the projected injection visit date will be calculated for each injection visit (excluding the 1st injection visit) as the injection visit date – the previous injection visit date plus 1 day minus 182 days. The number of days from the projected injection visit date will be classified into the following categories:

- < -14 days
- -14 to -8 days
- -7 to -3 days
- \pm 2 days
- 3 to 7 days
- 8 to 14 days
- > 14 days

The number and percentage of subjects in each category will be summarized for subjects in Treatment Groups 1 and 2 who receive SC injections for the injection visit of interest.

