4.2.2.2. Adherence to Once Daily Study Drug(s)

The adherence to once daily (QD) study drug(s) will be calculated based on 1 study drug for Treatment Groups 1, 2, and 4 (ie, F/TAF up to Week 28 and TAF or BIC from Week 28 onwards for Treatment Groups 1 and 2, and B/F/TAF for Treatment Group 4), and 2 study drugs for Treatment Group 3 (ie, oral QD LEN and F/TAF), excluding long acting LEN used for oral lead-in.

Adherence (%) of QD study drug(s) will be calculated as follows:

$$\begin{aligned} \text{Adherence (\%)} &= 100 \times \frac{\text{Total No. of pills taken}}{\text{Total No. of pills prescribed}} \\ &= 100 \times \frac{\sum \sum \text{No. of pills taken at each dispensing period for each study drug}^{[1]}}{\sum \sum \text{No. of pills prescribed at each dispensing period for each study drug}^{[2]}} \end{aligned}$$

- [1] Number of pills taken at a distinct dispensing period for QD study drug(s) will be calculated as the minimum of (a) the daily number of pills prescribed multiplied by the duration of treatment of QD study drug(s) at the dispensing period of the same dispensing date, and (b) the number of pills taken (number of pills dispensed minus the number of pills returned). Total number of pills taken is determined by summing the number of pills taken from all evaluable dispensing periods for all QD study drug(s).
- [2] Number of pills prescribed at a distinct dispensing period for QD study drug(s) will be calculated as the daily number of pills prescribed multiplied by the duration of treatment of QD study drug(s) at the dispensing period of the same dispensing date. Total number of pills prescribed is determined by summing the number of pills prescribed from all evaluable dispensing periods for all QD study drug(s).

The duration of treatment of QD study drug(s) at a dispensing period for the study drug is calculated as the minimum of (a) the last returned date of the study drug at a dispensing period, (b) date of premature discontinuation of the study drug, and (c) next pill dispensing date of the study drug, minus dispensing date of the study drug.

The next pill dispensing date is the following dispensing date of the study drug regardless of the bottle return date.

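### In the injection groups a missed or late lenacapavir injection never counts toward the Per-Protocol adherence exclusion, and an injection not given has no row in the SC adherence table

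*SAP*

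**What the plan says.** **PP set.** SAP 3.1.3 lists four exclusions: no on-treatment HIV-1 RNA in the Week 54 window (unless study drug was stopped for lack of efficacy), two eligibility violations, and "Nonadherence to once daily (QD) study drug(s): subjects with adherence rate for active once daily study drug(s) up to the Week 54 Visit", with the cut-off at the 2.5th percentile. None mentions the subcutaneous (SC) injection. SAP 6.1.3 uses this set to check the robustness of the primary analysis.

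**Pill adherence.** Under SAP 4.2.2.2 the rate "will be calculated based on 1 study drug for Treatment Groups 1, 2, and 4". The drug counted is "F/TAF up to Week 28 and TAF or BIC from Week 28 onwards for Treatment Groups 1 and 2". In Group 3 two drugs count, oral daily lenacapavir (LEN) and F/TAF.

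**Injection adherence.** SAP 4.2.2.1 assesses "adherence to the projected injection interval, which is 26 weeks (182 days) between 2 adjacent injection visits". The deviation is the injection date minus "the previous injection visit date plus 1 day minus 182 days". It is sorted into seven bands, the last being more than 14 days. The first injection visit is left out, and the table is "summarized for subjects in Treatment Groups 1 and 2 who receive SC injections for the injection visit of interest".

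**Dosing outside the window.** Protocol 5.3 foresees Group 1 and 2 participants not dosed within the visit windows. The sponsor must be contacted, "the participant may continue to receive GS-6207 with the approval of the Gilead medical monitor", and extra oral doses may be needed before the next injection.

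**The concern.** The PP analysis is the only robustness analysis of the primary endpoint built on adherence. The other two, Missing = Failure and Missing = Excluded in SAP 6.3.1, deal with missing data. A reader will take the PP result in Groups 1 and 2 to describe people treated as planned. As defined, it describes people who took the partner pill as planned, whatever happened with the long-acting injection. In Group 3 the same rule does include LEN, so it covers the investigational drug in the oral arm and not in the two injection arms.

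The SC table cannot fill the gap. Its denominator is people who were injected, so it describes the timing of injections given and not the proportion of due injections that were given.

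**Working it through.** The plan states no figure on this point, so the check traces its rules and applies its formula.

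**1. Does missing the Week 28 injection remove someone from the PP set?**
- Take a Group 1 or 2 participant who was injected on Day 15, is not injected at Week 28, takes every daily pill and has an RNA result at Week 54.
- Pills prescribed to Week 54: 28 × 7 + 26 × 7 = 196 + 182 = 378. Adherence by SAP 4.2.2.2 is 378/378 = 100%, so the pill rule does not apply.
- On-treatment status: SAP 3.8.1 sets the last dose date of an injected participant who stops early at the end date of the partner drug. SAP 6.1.1 counts RNA up to one day later. Missing the injection does not end on-treatment status, so the missing-RNA exclusion does not apply either.
- Result: the participant is per-protocol with 1 of the 2 injections planned before Week 54 (Day 15 and Week 28). A late Week 28 injection follows the same path.

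**2. What does the SC table show?** Deviation = gap in days + 1 − 182 (SAP 4.2.2.1), with nominal days from SAP Table 3-1 (Week 28 = 196, Week 54 = 378).

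| Situation | Gap (days) | Deviation | Band |
|---|---|---|---|
| Day 15 to Week 28, on schedule | 181 | 0 | ± 2 |
| Week 28 to Week 54, on schedule | 182 | +1 | ± 2 |
| 27 weeks | 189 | +8 | 8 to 14 |
| Exactly 28 weeks | 196 | +15 | > 14 |
| 30 weeks | 210 | +29 | > 14 |
| Week 28 skipped, next injection at Week 54 | 363 | +182 | > 14 |
| Week 28 skipped, no later injection | none | none | no row |

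Late second and later injections are visible. A skipped injection has no row at its own visit; it shows up later only if another injection follows. A late first injection cannot appear, because that visit is excluded. An injection at exactly 28 weeks, inside the 26 to 28 week interval of Protocol 6.3.4, lands in the latest band because of the added day.

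**3. Size.**
- Protocol 1.2.2.8 reports 105 treated SC-group participants, of whom 103 received an injection: 105 − 103 = 2 never injected. The number who missed or were late for Week 28 is not given.
- One participant is 1/52 = 1.9% of a 52-person arm.
- As an illustration, Group 1's reported 47/52 (90.4%) becomes 46/51 (90.2%) if one responder is removed and 47/51 (92.2%) if one non-responder is removed. These are Full Analysis Set counts; PP counts are not in the documents.
- For scale, the pill rule marks about 0.025 × 105 = 2.6 SC-group participants, if the percentile is taken in that group.

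**The case against.** **Late injections are recorded.** A reader might infer that a very late injection is nowhere treated as non-adherence, or that the SC table can show full adherence however many injections were missed. The documents do not support this. SAP 4.2.2.1 has a band for more than 14 days, and a skipped visit followed by a later injection falls into it. Only an injection with no successor disappears completely.

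**Never-injected participants mostly leave the PP set.** A reader might infer that someone who never received the Day 15 injection stays in. Protocol 6.4.1.1.1 sends a participant who declines it to early termination. For non-injected participants who discontinue, SAP 3.8.1 takes the earliest last dose of any study drug, so the oral lead-in can set the date. There is then no on-treatment Week 54 RNA, and the first PP exclusion applies unless the reason was lack of efficacy. The 2 never-injected participants are probably of this kind, though the documents do not say.

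**Injections are visible elsewhere.** SAP 7.1.7.1 counts recipients at each injection visit, SAP 4.2.2.2 lists administration by participant, SAP 4.3 summarises important deviations, and SAP Appendix 3 classifies oral reload before the first injection. This stands, but none of it changes PP membership or gives the number due.

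**Version.** The SAP rests on protocol amendment 3. The protocol supplied is later: it reports Week 54 results and has an oral bridging column that the SAP's schedule lacks. Whether the 28-week limit was in amendment 3 cannot be seen. It also cannot apply to Day 15, which has no previous injection.

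**Weight.** The trial is called non-confirmatory (SAP 3.5), and the PP analysis is secondary. That limits the consequence but does not remove the gap.

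**Conclusion.** The point holds in two limited parts. First, in Groups 1 and 2 a missed or late injection never counts toward the PP adherence exclusion. An injected participant who misses or is late for Week 28, continues the partner drug and has a Week 54 RNA stays per-protocol, while Group 3 is judged partly on LEN itself. Second, an injection not given has no row at its visit in the SC adherence table, and none at all if no later injection follows.

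The number of such participants is unknown, so the effect on the PP estimate cannot be stated. The illustration in Group 1 is a change of −0.2 to +1.8 points per participant removed. A reader might infer that the primary result is affected. It is not, because the snapshot analysis on the Full Analysis Set does not use this rule. The conclusion assumes that the last-dose and on-treatment definitions are applied as written.

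**What to change.** - **SAP 3.1.3:** for Groups 1 and 2, add an exclusion for a Week 28 injection not given while on study drug, or given outside the injection interval of the protocol version in force without oral LEN cover. Add a separate criterion for the Day 15 injection, based on its scheduled visit.
- **SAP 4.2.2.1:** use as denominator all Group 1 and 2 participants on study drug when the injection falls due, and add a not-given row. Align the day formula and the bands with the protocol interval, so that an injection inside it is not classed with the latest ones.
- **Timing:** Week 54 results are already reported, so label any Week 54 rerun post hoc and document it in the clinical study report, as SAP Section 1 requires for changes after finalization. Pre-specify the criteria for any later PP or SC adherence analysis, such as Week 80.

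The cost is SAP wording and a derived flag. Injection dates are already collected on the Study Drug Administration eCRF. The PP set becomes slightly smaller, and the added exclusion, like the pill rule, conditions on events after randomization. The primary analysis is untouched.

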BIC, B = bicitegravir; B/F/TAF = bicitegravir/emtricitabine/tenofovir alafenamide (coformulated; Biktarvy[®], BVY); BL = baseline; F/TAF = emtricitabine/tenofovir alafenamide (coformulated; Descovy[®]); GS-6207 = lenacapavir, LEN; PK = pharmacokinetic; QD = once daily; Q6M = every 6 months; SC = subcutaneous; TAF = tenofovir alafenamide; Tx-naive = treatment naïve; Wk = week

Disposition and Baseline Characteristics

Of the 249 participants screened, 183 were randomized, and 182 received at least 1 dose of study drug. Of these 182 participants, 22 participants (12.1%) prematurely discontinued the study drug during the Main Phase (ie, data collected on or before Week 80): 17 of 105 participants (16.2%) in the SC GS-6207 total group, 4 of 52 participants (7.7%) in the oral GS-6207 group, and 1 of 25 participants (4.0%) in the bicitegravir/emtricitabine/tenofovir alafenamide (coformulated; Biktarvy[®]; BVY) group. The reasons for premature study drug discontinuation in the SC GS-6207 total group were participant decision and lost to follow-up (each 4 participants [3.8%]), investigator’s discretion, lack of efficacy, and AE (each 3 participants [2.9%]). The reasons for premature study drug discontinuation in the oral GS-6207 group were lost to follow-up (3 participants [5.8%]) and participant decision (1 participant [1.9%]) and in the BVY group it was participant decision (1 participant [4.0%]).

As of the Week 54 data cut date, 8 participants entered into the Extension Phase (SC GS-6207 total group, 5 participants; oral GS-6207 group, 3 participants) and were continuing study drug.

Demographics, general baseline characteristics, and baseline disease characteristics are described in the Interim Week 28 CSR.

Demographic and baseline characteristics were similar across the treatment groups. Most participants were male (93.4%), cisgender (92.3%), and gay (69.8%). Median age was 29 years (range: 19–72 years). Race was balanced between Black versus non-Black (52.2% vs 47.8%, respectively), as was ethnicity between Hispanic or Latino versus not Hispanic or Latino (45.1% vs 54.9%, respectively).

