1.2. Study Design

Design Configuration and Subject Population

This is a Phase 2, randomized, open label, active controlled, multicenter study.

Approximately 175 treatment-naive PWH who meet all eligibility criteria will be randomized in a 2:2:2:1 ratio to 1 of the following 4 treatment groups. Randomization will be stratified by HIV-1 RNA level ($\leq 100,000$ copies/mL or $> 100,000$ copies/mL) at screening.

Treatment Groups

Treatment Group 1 (n = 50)

Induction: Subjects will receive oral LEN 600 mg, 600 mg, and 300 mg, without regard to food, at Days 1, 2, and 8 respectively. Subjects will also begin oral daily emtricitabine (F)/TAF (200/25 mg), without regard to food from Day 1 onwards for a total of 28 weeks. On Day 15 subjects will receive subcutaneous (SC) LEN 927 mg, without regard to food.

Maintenance: Subjects will receive SC LEN 927 mg at Week 28 and every 26 weeks thereafter. Subjects will discontinue oral daily F/TAF (200/25 mg) at Week 28 and begin taking oral daily TAF (25 mg), without regard to food.

Treatment Group 2 (n = 50)

Induction: Subjects will receive oral LEN 600 mg, 600 mg, and 300 mg, without regard to food at Days 1, 2, and 8 respectively. Subjects will also begin oral daily F/TAF (200/25 mg), without regard to food from Day 1 onward for a total of 28 weeks. On Day 15 subjects will receive SC LEN 927 mg, without regard to food.

Maintenance: Subjects will receive SC LEN 927 mg at Week 28 and every 26 weeks thereafter. Subjects will discontinue oral daily F/TAF (200/25 mg) at Week 28 and begin oral daily BIC (75 mg) without regard to food.

Treatment Group 3 (n = 50)

Subjects will receive oral LEN 600 mg and 600 mg without regard to food at Days 1 and 2, respectively. On Day 3, subjects will begin oral daily LEN 50 mg, without regards to food. Subjects will begin oral daily F/TAF (200/25 mg), without regard to food from Day 1 onwards.

Treatment Group 4 (n = 25)

Subjects will receive oral daily bictegravir/emtricitabine/TAF (B/F/TAF, 50/200/25 mg), without regard to food at Day 1 and throughout their participation in the study.

Key Eligibility Criteria

Treatment naive PWH who meet the following criteria:

- Age \geq 18 years of age at Screening
- Plasma HIV-1 RNA \geq 200 copies/mL at Screening
- CD4+ cell count \geq 200 cells/ μ L at Screening

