For a record where the number of pills returned was missing (with “Yes” answered for “Was Bottle returned?” question), it is assumed the number of pills returned was zero. If the number of pills dispensed was missing or any study drug bottle was not returned or the bottle return status was unknown, all records in that dispensing period for that study drug will be excluded from both denominator and numerator calculation.

Adherence will be calculated for each subject for the entire dosing period up to the date of permanent discontinuation of the study drug for subjects who prematurely discontinued study drug or using all available data for subjects ongoing on study drug by the data cut date.

Descriptive statistics for adherence (n, mean, SD, median, Q1, Q3, minimum, and maximum) along with the number and percentage of subjects belonging to adherence categories (eg, < 80%, ≥ 80% to < 90%, ≥ 90% to < 95%, ≥ 95%) will be provided for subjects who return at least 1 bottle of randomized QD study drug, and who have calculable adherence in the Safety Analysis Set. No inferential statistics will be provided.

A by-subject listing of study drug administration and drug accountability will be provided separately by subject ID number (in ascending order) and visit (in chronological order).

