6.1.3. Secondary Analysis for the Primary Efficacy Endpoint

A secondary analysis based on the Week 54 PP analysis set will also be performed to evaluate the robustness of the primary analysis of the primary endpoint. Subjects excluded from the Week 54 PP analysis set will be determined before database lock.

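### The Per-Protocol nonadherence criterion is a rank cut: it flags about 4 of 182 participants whatever adherence was, so PP/FAS agreement is weak evidence of robustness to nonadherence

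*SAP*

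**What the plan says.** SAP 3.1.3 builds the PP set by subtraction: "This analysis set includes all subjects in the FAS excluding subjects meeting any of the following criteria". The fourth criterion, labelled nonadherence to once-daily study drug, removes "subjects with adherence rate for active once daily study drug(s) up to the Week 54 Visit below the 2.5th percentile". It gives no minimum adherence. It does not say whether the percentile is pooled or taken within treatment group, over which set, or how ties and participants without calculable adherence are handled.

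SAP 6.1.3 gives the purpose. The PP analysis "will also be performed to evaluate the robustness of the primary analysis of the primary endpoint", and "Subjects excluded from the Week 54 PP analysis set will be determined before database lock".

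SAP 4.2.2.2 defines adherence as pills taken divided by the sum of the "No. of pills prescribed at each dispensing period for each study drug", with pills taken capped at pills prescribed in each dispensing period. The same section plans a descriptive table of the "number and percentage of subjects belonging to adherence categories (eg, < 80"%, then 80 to < 90%, 90 to < 95% and ≥ 95%). Those bands are not tied to any efficacy analysis. The other analyses of Week 54 response do not use adherence either: SAP 6.3.1 deals with missing HIV-1 RNA, and the subgroups in SAP 3.4.1 are age, sex, race, baseline HIV-1 RNA and baseline CD4 count.

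**The concern.** The criterion is named for a behaviour but defined by rank within the trial. Someone in the lowest 2.5% is called nonadherent even if they took nearly every pill. Someone who missed a third of their pills stays in if enough others did worse. The PP analysis is the only planned check on the primary endpoint that takes adherence into account. If its adherence criterion does not respond to the amount of nonadherence, a PP result close to the Full Analysis Set (FAS) result would be expected whether adherence was excellent or poor, and a reader could take more reassurance from it than it can give.

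**Working it through.** **Inputs.** Planned: "Approximately 175 treatment-naive PWH who meet all eligibility criteria will be randomized in a 2:2:2:1 ratio" (SAP 1.2; 50/50/50/25). Actual: "Of the 249 participants screened, 183 were randomized, and 182 received at least 1 dose of study drug" (Protocol 1.2.2.8), with 52, 53, 52 and 25 in the four groups. The percentile is 0.025 and the exclusion is strictly below it. The documents give no adherence distribution, so the shares of participants below 80% used here are assumptions, varied from 0% to 30%.

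**The plan's own figures.** The SAP states no expected number of PP exclusions, so there is none to reproduce. Its one design figure, 39% power (SAP 1.3), reproduces: Φ(0.12/√(0.909 × 0.091 × (1/50 + 1/25)) − 1.96) = 39.9%. Nothing below depends on it.

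**Step 1: number flagged, pooled.** Under the SAS default definition, when 0.025 × n is not an integer the percentile is the next order statistic.
- n = 182: 0.025 × 182 = 4.55, so the cut is the 5th lowest value and 4 people lie below it.
- n = 175: 0.025 × 175 = 4.375, so again 4.
- With linear interpolation, 5 at either n.

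**Step 2: number flagged, within group.**
- SAS default: 0.025 × 52 = 1.3, 0.025 × 53 = 1.325 and 0.025 × 25 = 0.625, giving 1 + 1 + 1 + 0 = 3, none from B/F/TAF.
- Linear interpolation: 2 + 2 + 2 + 1 = 7.

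The one sentence in the SAP therefore supports PP sets that differ by 3 to 7 flagged participants.

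**Step 3: does the count respond to adherence?** n = 182, pooled, SAS default. Nonadherent participants are assumed uniform on 40–80% and the rest uniform on 90–100%.

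| Share below 80% | People below 80% | Flagged by percentile | Flagged and below 80% | Below 80% left in by this criterion | Excluded by a < 80% cut |
|---|---|---|---|---|---|
| 0% | 0 | 4 | 0 | 0 | 0 |
| 1% | 2 | 4 | 2 | 0 | 2 |
| 2.5% | 5 | 4 | 4 | 1 | 5 |
| 5% | 9 | 4 | 4 | 5 | 9 |
| 10% | 18 | 4 | 4 | 14 | 18 |
| 20% | 36 | 4 | 4 | 32 | 36 |
| 30% | 55 | 4 | 4 | 51 | 55 |

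The constant 4 follows from ranking and does not depend on the assumed distributions. In the first row all four flagged people are above 90%. Some nonadherent people stay in once there are more than 4, and more than half stay in once there are 9 or more (9/182 = 4.9%).

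**Step 4: what lowers the count.** Because pills taken are capped, ties at 100% can occur. They matter only in the extreme: with 99% of participants at 100% the count falls to 2, and with everyone at 100% it is 0. Participants without calculable adherence cannot be flagged. Anyone already removed by the first PP criterion (no on-treatment Week 54 HIV-1 RNA, unless missing because study drug was stopped for lack of efficacy) is not an additional exclusion.

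**The case against.** **The rule is not inert.** A reader might infer that it can show nothing about nonadherence. That is too strong. It tests the effect of dropping the lowest 2.5%, which would be nearly enough if nonadherence were no commoner than that; at 5% it still catches 4 of 9. It could also move an estimate: if all four flagged were Group 1 non-responders, 47/52 (90.4%) would become 47/48 (97.9%).

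**The loss cannot be sized in response points.** A reader might try. Assume 50% response below 80% adherence and 95% otherwise. With 15% below 80%, the FAS rate is 0.15 × 0.50 + 0.85 × 0.95 = 88.25%. The percentile rule gives (0.8825 × 182 − 4 × 0.50)/178 = 89.1%, and the < 80% cut gives 95.0%. The rule then shows about 0.9 of 6.75 points. With 5% below 80% the same formulas give 92.75%, 93.7% and 95.0%, or 1.0 of 2.25 points. The answer changes with inputs that the documents do not supply. These are also single-group rates, and shifts common to both arms would largely cancel in the planned between-group difference. They also ignore the other PP criteria. Protocol 1.2.2.8 reports 22 premature discontinuations, 3 of them for lack of efficacy. Some of the other 19 would leave under the first criterion, though dates are not given. Such figures should not be presented as the effect on the PP comparison.

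**Other points for the plan.** SAP 6.1.3 speaks of robustness in general, not of isolating nonadherence. The < 80% band is only an example category in a descriptive table, and no passage justifies it as a PP threshold. If adherence is high, an absolute cut excludes nobody; if poor, it makes larger post-randomisation exclusions in an open-label trial with 25 controls. These points stand, and they are why a supplementary analysis is an acceptable alternative.

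It can also be said that the descriptive bands let a reader judge whether trimming 2.5% was enough. That holds only in part: the table runs to the data cut or discontinuation rather than to Week 54, uses the Safety Analysis Set, and is not linked to response.

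**Conclusion.** The concern holds in limited form. The fourth PP criterion flags about 4 of 182 participants if pooled under the SAS default, 3 to 7 across other readings, and fewer with ties or overlap with the first criterion, whatever the level of adherence. It measures sensitivity to trimming the lowest 2.5%. If nonadherence is commoner than that, nonadherent participants stay in the PP set, and they are the majority of the nonadherent from about 5% upward. If adherence is high, the rule drops adherent participants. PP/FAS agreement is then weak evidence, though not zero evidence, of robustness to nonadherence.

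The fixed count rests only on the definition of a percentile and on n. The share left in rests on an assumed frequency of adherence below 80%, which the documents do not give. They support no figure for the effect on the PP treatment difference. The stakes are moderate: this is a supportive analysis in a trial that SAP 3.5 calls non-confirmatory, with tests for descriptive purposes (SAP 3). It should be corrected, but the primary analysis does not depend on it.

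**What to change.** In SAP 3.1.3, do one of the following:

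1. Replace the percentile with an absolute cut: exclude participants whose once-daily adherence up to the Week 54 visit is < 80%, the lowest band in SAP 4.2.2.2, applied identically in all four groups.
2. Keep the percentile rule, state that it is pooled and over which set, describe it as trimming the lowest 2.5%, and add the < 80% exclusion as a labelled supplementary PP analysis.

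Under either option, report the number excluded by this criterion in each group and say how participants without calculable adherence are treated, since neither cut can classify them.

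**Cost.** One line of text and one derivation (adherence truncated at Week 54) from data already collected. The PP set size is no longer fixed in advance and may be smaller if adherence is poor. The SAP was signed in October 2021 and the current protocol already reports Week 54 results, so for that time point the change would be post hoc. Option 2 fits better there, documented in the CSR as SAP 1 requires for changes after finalization. For any later PP analysis the absolute cut can still be prespecified.
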